### DATA COLLECTION AND QUALITY ASSURANCE

The only people who will know that these patients are research participants are members of the research team. No information about them, or provided by them during the research, will be disclosed to others without their written permission, except if it is necessary to protect their rights or welfare (for example, in case of injury or emergency care), or if it is required by law. When the results of the research are published or discussed in conferences, no information will be included that would reveal the identity of these patients. All data will be kept in locked files, and subjects will be identified by codes when the data gathered in this procedure is presented or published. Authorized representatives of the National Institutes of Health may need to review records of individual participants. As a result, they may see their name; but they are bound by rules of confidentiality not to reveal the patients' identity to others. Blood samples for measurement of serum naringenin concentrations will be shipped by the Clinical Chemistry Core to [name] at the University of Tennessee. Serum naringenin concentrations will be measured at the University of Tennessee by a validated high performance liquid chromatographic method using solid phase extraction.

### Privacy

The subjects will be interviewed in the privacy of an exam room and their records will be protected by a secure medical records area and a password-protected electronic database monitored by the Pennington Research Computing group. Subjects will be asked to sign a written consent after reading it, having it reviewed with them by the study staff and having all their questions answered. The consent conversation will be conducted in the privacy of an exam room and the subject will be allowed to take the consent home to discuss their decision with their family or counselor, if desired. Study procedures will be conducted by trained staff in accordance with PBRC outpatient and inpatient clinic standards of practice and with subjects' informed consent. Confidential subject information including medical records and test results will

be available only to persons authorized by the Pennington. Information collected from subjects will be the minimum amount of data necessary to accomplish the research purposes.

### **Data and Specimen Management**

Study participants will be assigned unique subject identification (ID) numbers. Study subject ID numbers will be used on all data collection instruments, to include questionnaires, data collection forms, biological specimen tubes, and computer records. A master list linking the participants' names and ID numbers will be kept in a password-protected computer file with access restricted to the PI and co-PI's. Biological samples that are moved off-site for analysis will not contain any personally identifiable information and will be labeled with only the unique subject ID numbers. Staff at these sites will not have access to the master list at any time.

Data collection forms will be kept under lock and key, or password-protected if computerized, and under the control of the PI, co-PIs, and medical investigator. Only personnel assigned to the research study by the PI will have access to the data. Hard-copy data records will be stored for a minimum of 3 years.

The PBRC has a fully integrated, campus-wide, automated data management system. All data are entered into a central database using existing methodology that has been fully validated and undergoes continuous quality assurance by the PBRC Research Computing Core and the nutrition and obesity research center (NORC). All data are backed up daily, and the Research Computing Core at the PBRC oversees all data management. The research team has extensive experience using the procedures and methods required to conduct this study. Standard operating procedures in place throughout the units at Pennington Biomedical will be utilized for repeatable, valid data collection and quality.

In accordance the standards of practice followed by the Clinical Chemistry core, blood samples will be stored frozen at PBRC until analysis can be completed. Specific blood samples will be shipped to University of Tennessee for further analysis. Packaging and shipping of biological samples will be overseen by the PI, shipped by the laboratory and will be completed in accordance with International Air Transport Association regulations to ensure that viable biological samples reach their intended destination.

### **WITHDRAWAL OF SUBJECTS**

We will attempt to retain program participants once randomized for study completion through the end of study visit. It is our desire to analyze results on all participants who were enrolled in the study. In accordance with the declaration of Helsinki/Tokyo/Venice/Hong Kong, participants have the right to withdraw from the program at any time for any reason. The investigator also has the right to withdraw participants from the program treatments in the event of inter-current illness, adverse experience, treatment failure, protocol violation, or other reasons. Should a participant decide to withdraw from treatment, all efforts will be made to complete and report follow-up observations as thoroughly as possible.

### **RISKS/BENEFITS**

The study involves the following risks:

- **IV Procedures/Blood Draws:** There is the possibility of discomfort, pain, and bruising at the vein on the arm where the needle is inserted. There may also be a small risk of bleeding and a very small risk of infection at the site of the blood draw. Sterile technique and trained personnel minimize these risks.
- **Dietary Supplement.** Naringenin is a component of food and is marketed in the US as a dietary supplement. The naringenin extract is from Gencor Lifestage Solutions, GE

Nutrients Inc. (Irvine, CA), a reputable supplier of botanical extracts and supplements. The extract from *Citrus Senensis* (sweet oranges) has been characterized using high performance liquid chromatography, (HPLC), thin layer HPLC (HPTLC), and Liquid chromatography-mass spectrometry (LC-MS). The details of the extraction process, characterization of the extract, certificate of analysis, specifications, and materials safety data sheet are provided in the Protocol Supplemental Info. Cellulose, used for the placebo, will be encapsulated in identical opaque capsules as the naringenin extract. The naringenin extract and placebo containing capsules will be prepared and dispensed by the PBRC pharmacist.

The literature is replete with the beneficial effects of naringenin in obesity, cardiovascular disease, and cancer. However, grapefruit has been shown to increase the bioavailability of drugs administered orally. Several compounds in grapefruit including the flavonoids (naringin and naringenin), furanocoumarins (bergamottin) and sesquiterpens have been implicated. Naringenin being polyphenolic and high in electrons, can theoretically inhibit cytochrome P 450 enzymes and enhance the bioavailability of medications such as statin drugs. Although inhibition of the cytochrome P 450 enzyme system has been demonstrated in vitro, the results of in vivo studies suggest that naringenin is not the main inhibitory compound in grapefruit. Additionally, naringin has been shown to inhibit the enteric organic anion-transporting polypeptide in vitro, and reduce the bioavailability of an antihistamine. The supplement may also adversely affect subjects with citrus allergies. However, subjects taking chronic medications or having citrus allergies are excluded from the study, and over the counter medications must be stopped 72 hours prior to the test day.

- **Meals.** There is no risk associated with the meals provided by the Pennington Metabolic kitchen. Additionally, subjects will be asked to inform staff about any food allergies or intolerances. A dietary questionnaire is routinely administered at the screening visit when the study involves a meal service. Research dietitians are responsible for managing the dietary component of specific study protocols. A continuous quality assurance program is followed to check food item weights, recipe procedures, packed meal and tray assembly, and food temperatures. Documentation is maintained for each study. All Metabolic Kitchen staff members receive training in food sanitation and in research diet preparation.
- **Anthropometric Measurements and Vital Signs.** The PBRC outpatient and inpatient clinic staff are trained to perform these procedures in accordance with PBRC standards of practice. There are no risks involved.
- **Urine Test.** The staff of the phlebotomy unit collect the urine in accordance with standard operating practices. There are no risks involved.

In addition to the risks listed above, participants may experience a previously unknown risk or side effect.

#### **Minimizing risks**

Continuous monitoring by the PI and/or the medical investigator of the study will minimize all potential risks and discomforts. Research participants will be immediately withdrawn from the study upon evidence of any significant adverse event.

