The maximum recommended starting dose (MRSD) for naringenin may be estimated at approximately 135 mg since no adverse events were reported at this dose. The dose escalation scheme recommended for first in human studies is rapid dose escalation initially (MRSD x 2) until the estimated effective dose (600 mg) is reached and then at a more cautious escalation (e.g. x 1.5). The first dose will be 150 mg, the MRSD for the practical purpose of preparing the capsule of an extract from oranges which contains 30% naringenin (Gencor Lifestage Solutions, GE Nutrients Inc., Irvine, CA). HPLC and mass spectrometry verification using a second standard to quantify the naringenin in the extract was conducted by the Rutgers University Botanical core. It was determined that the extract contains 27% naringenin by one method and 29% naringenin by a second method. Therefore, the amount of extract for the 150 mg, 300 mg, 600 mg, and 900 mg doses of naringenin will be calculated based on the average of 28%. According to the United States Department of Agriculture (USDA) database for the flavonoid content of selected foods 150 mg of naringenin could be found in a minimum of approximately four oranges and a maximum of 12 oranges. The orange extract will be calculated to deliver 150 mg, 300 mg, 600 mg, and 900 mg of naringenin. The capsules will be prepared and dispensed by the PBRC pharmacist. The schedule for dosing is provided in Table 1.

Table 1. Ascending Oral Dose Schedule			
	Visit 1	Visit 2	Visit 3
Cohort 1			
Sequence 1 (n=3)	150 mg	Placebo	300 mg
Sequence 2 (n=3)	150 mg	300 mg	Placebo
Sequence 3 (n=3)	Placebo	150 mg	300 mg
Cohort 2			
Sequence 4 (n=3)	600 mg	Placebo	900 mg
Sequence 5 (n=3)	600 mg	900 mg	Placebo
Sequence 6 (n=3)	Placebo	600 mg	900 mg

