## **STATISTICAL CONSIDERATIONS**

As comparative efficacy of the doses of the extract is not the primary issue in this protocol, power to detect efficacious effects is not specifically evaluated to justify sample sizes. A sample of 18 subjects (three subjects in each of three treatment sequences in each of two cohorts) will be enrolled in the ascending single dose evaluation. Thus, all nine subjects in Cohort 1 will receive the placebo and both 150 and 300 mg doses of the extract; similarly all 9 subjects in Cohort 2 will receive the placebo and both 600 and 900 mg doses of the extract. Before the next cohort is commenced, subjects in the preceding cohort must have received all three treatments and the safety and tolerability data must have been assessed showing tolerance to the doses of naringenin. Based on the pharmacokinetic study done in humans, the sample size (n=6, at each dose) is sufficient to provide a pharmacokinetic profile of naringenin in serum.

The primary outcome will be to determine the effect of the naringenin extract on safety and tolerability based on clinical and biochemical assessment.

The secondary outcome will be to determine the pharmacokinetics of naringenin at the 150 mg and 600 mg doses. Serum concentrations of naringenin will be obtained to assess drug exposure.

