### **Safety and tolerability.**

Dose safety will be investigated by compiling by treatment (e.g. 150 mg dose, 300 mg dose, placebo) a list of adverse events such as frequency of headaches, nausea, vomiting. The study physician in consultation with the coordinator will review and determine safety and tolerability. The frequency of these events will be counted and compared with the placebo group. The

cohorts will be run in series. There will be an interval of up to four weeks between the two cohorts. During this time an interim analysis will be conducted and a safety summary of adverse events for Cohort 1 will be compiled and reviewed by the investigators.

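### Withdrawal after a significant AE thins the later periods, so AE counts at 300 and 900 mg need denominators and a companion figure over all randomised

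*Combined protocol and SAP*

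**What the plan says.** Four parts of the combined protocol and SAP bear on this.

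- **Withdrawal.** Minimizing risks makes removal automatic: "Research participants will be immediately withdrawn from the study upon evidence of any significant adverse event". The word significant is not defined there and is not one of the intensity grades (mild, moderate, severe). Withdrawal of Subjects is worded as a discretion: "The investigator also has the right to withdraw participants from the program treatments in the event of inter-current illness, adverse experience".
- **Order of treatments.** In "Table 1. Ascending Oral Dose Schedule", write L for the lower dose, H for the higher and P for placebo. The sequences in each cohort are L-P-H, L-H-P and P-L-H, with three subjects each.
- **Exposure.** Statistical Considerations assumes full exposure: "Thus, all nine subjects in Cohort 1 will receive the placebo and both 150 and 300 mg doses of the extract". It says the same of Cohort 2 at 600 and 900 mg.
- **Analysis.** Safety and tolerability says "Dose safety will be investigated by compiling by treatment (e.g. 150 mg dose, 300 mg dose, placebo) a list of adverse events", and then "The frequency of these events will be counted and compared with the placebo group". It gives no denominator and no handling of periods that were never given. No replacement of withdrawn subjects is described.

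**The concern.** A subject withdrawn for a significant AE on 150 or 600 mg never takes 300 or 900 mg, and in two of the three sequences never takes placebo either. The group that supplies the higher-dose figure is therefore selected on the outcome being measured, which is the primary outcome. A reaction at the lower dose can only reduce the number of events later counted at the higher one. If the same people tend to react at both doses, the apparent rise with dose shrinks and may vanish. A table of counts would then make the top dose of a cohort look better tolerated than it is. The Cohort 1 summary is also what the investigators review before Cohort 2 begins.

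**Working it through.** **1. The plan's own figure.** Statistical Considerations: "A sample of 18 subjects (three subjects in each of three treatment sequences in each of two cohorts) will be enrolled". 3 × 3 × 2 = 18, so there are 9 subjects per cohort and 9 planned periods per treatment. This reproduces. No AE rate, alpha or power is stated for safety, so every AE rate and correlation below is an assumption.

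**2. Who can be lost before each treatment (Table 1).** L precedes H in 9 of 9 subjects per cohort. P follows L in 6 of 9 (after both doses in 3) and comes first in 3 of 9.

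**3. Chance of losing someone after the lower dose.** With rate p₁ of significant AEs on L, this is 1 − (1 − p₁)⁹.

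| p₁ (assumed) | At least 1 of 9 lost | Expected number reaching H, 9(1 − p₁) |
|---|---|---|
| 3% | 24% | 8.73 |
| 5% | 37% | 8.55 |
| 10% | 61% | 8.10 |
| 20% | 87% | 7.20 |

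These figures ignore withdrawals during placebo.

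**4. Counts, with independent events.** Assume significant-AE rates of 5% (P), 15% (L) and 25% (H).

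- Subjects reaching H: 3 × (0.85 × 0.95 + 0.85 + 0.95 × 0.85) = 7.395. Expected events: 7.395 × 0.25 = 1.85, against 9 × 0.25 = 2.25 with nobody withdrawn.
- Subjects reaching P: 3 × (0.85 + 0.85 × 0.75 + 1) = 7.46. Expected events: 7.46 × 0.05 = 0.37, against 0.45.
- The count difference H − P is 1.85 − 0.37 = 1.48, against 2.25 − 0.45 = 1.80.

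So raw counts are lowered even without within-subject correlation. The rates among those dosed stay at 25% and 5%.

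**5. Rates, with correlated events.** Use a bivariate-normal threshold model with margins p₁ and p₂ and joint probability p₁₂. The observed higher-dose rate among those not withdrawn is (p₂ − p₁₂)/(1 − p₁). Cumulative non-tolerance over all randomised is p₁ + p₂ − p₁₂.

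| p₁ / p₂ | Latent correlation | p₁₂ | Observed at H | Cumulative |
|---|---|---|---|---|
| 15% / 25% | 0 | 0.0375 | 25.0% | 36.3% |
| 15% / 25% | 0.5 | 0.0817 | 19.8% | 31.8% |
| 15% / 25% | 0.8 | 0.1189 | 15.4% | 28.1% |
| 3% / 6% | 0.5 | 0.0095 | 5.2% | 8.1% |

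In the limit where the same people react at both doses, 15%/25% gives (0.25 − 0.15)/0.85 = 11.8%, below the lower dose's own 15%.

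**6. Contrasts under the actual sequences.** Simulation of Table 1 with the withdrawal rule and 5/15/25%, in percentage points. The true values are L − P = 10, H − P = 20 and H − L = 10.

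| Correlation | L − P, all dosed | H − P, all dosed | H − L (by subtraction) | L − P, pairs only | H − P, pairs only |
|---|---|---|---|---|---|
| 0 | 10.0 | 20.0 | 10.0 | 2.8 | 16.5 |
| 0.5 | 11.0 | 15.7 | 4.7 | 3.6 | 12.8 |
| 0.8 | 11.5 | 12.6 | 1.1 | 3.9 | 10.2 |

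*Pairs only* restricts to subjects who received both treatments. It is further from the truth than the by-treatment rates in every row. A subject in four of the six sequences reaches placebo only by having had no significant AE on the lower dose, so those events are zero by construction in 6 of 9 potential pairs.

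**7. Second model.** A logistic model with a subject random intercept, applied to the Table 1 sequences, gives the same picture. The H − P count difference was understated in all 20 scenarios. Rates and risk differences were understated whenever the random-intercept SD exceeded 0, and were unbiased at SD 0. At assumed 10/20/30% and SD 3, H − L moved from +10 to −0.6 points. At assumed 5/10/20% and SD 2, the H/P risk ratio went from 4.00 to 4.34, so it was not understated.

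**The case against.** The strongest reply has four parts.

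- **Rates.** The rates of 15% and 25% are high for this compound. The dose rationale reports no AEs in 6 subjects at 135 mg, nor in 18 given a single 1000 mg dose with a bioavailability enhancer. At a true 25%, none in 18 has probability 0.75¹⁸ = 0.6%. Population and formulation differ, but at 3%/6% the bias is under one point and there is a 0.97⁹ = 76% chance that nobody is lost after the lower dose. This stands, and it limits the size.
- **Noise.** With 9 subjects, the standard error of a 25% rate is √(0.25 × 0.75/9) = 14 points, against a bias of about 5 points at correlation 0.5. This also stands. But the bias has a known direction when correlation is positive, and it costs almost nothing to expose.
- **Scope.** Only significant AEs remove anyone, while the summary covers all AEs, including headache and nausea. This stands: it would be wrong to infer that the higher doses are seen only in people who tolerated the lower dose without any event.
- **Oversight.** A physician reviews the list, no safety test is planned, and a withdrawal among nine subjects would be noticed. Cohort 2 uses new subjects, so nothing carries over from 150 to 900 mg. This lowers the risk of misreading, but a published table of counts would still not show the loss. The event-count stopping rules need two or more subjects with the same event, so a single withdrawal need not halt dosing, although the investigator may call a review.

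Continued follow-up and the stated wish to analyse everyone enrolled do not help, because neither produces data on a treatment not taken.

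**Conclusion.** The concern holds in a conditional form. Followed as written, the plan lets earlier withdrawals remove subjects from the 300 and 900 mg summaries and from much of placebo, and it does not show that this has happened. Expected raw higher-dose counts fall whenever there are earlier withdrawals. Higher-dose rates and the higher-minus-lower difference are understated if AE proneness is positively correlated within subject, which is plausible but assumed. At 15%/25% the observed higher-dose rate runs from 25% (correlation 0) to 19.8% (0.5) and 15.4% (0.8). At 3%/6% and correlation 0.5 it is about 5% against 6%. If no significant AE occurs, there is no effect.

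A reader might infer that the planned comparison must understate the dose effect. The documents do not support that. Rates are unbiased when events are independent, placebo is depleted too, the higher-dose/placebo risk ratio can be unchanged or overstated, and lower-minus-placebo can be slightly overstated. A reader might also infer that a within-subject placebo contrast would cure the problem. Under this withdrawal rule it selects tolerators more strongly than the planned comparison does.

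**What to change.** In Safety and tolerability, before unblinding:

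1. For each dose and placebo, show the number of subjects dosed and the number with an AE. List each withdrawal by the treatment that triggered it.
2. For 300 and 900 mg, add cumulative non-tolerance over all subjects randomised in the cohort. Count a subject withdrawn for an AE on the lower active dose as not tolerating the higher one, and show withdrawals on placebo separately. Label the figure as conservative when lower-dose events would not have recurred (31.8% against a true 25% at correlation 0.5). With non-negative correlation, and apart from placebo-period losses, it and the rate among those dosed bracket the true rate on average.
3. Do not use a placebo contrast restricted to subjects with both periods.
4. Reconcile the automatic wording in Minimizing risks, the discretionary wording in Withdrawal of Subjects, and the statement in Statistical Considerations that all nine subjects receive all three treatments. State what significant means, so that the affected events can be identified. Which withdrawal rule applies is for the investigators to decide.

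The cost is extra table columns with no new data, and a less favourable top-dose figure if anyone is withdrawn.

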#### **Potential Benefits**

There is no direct benefit to the volunteers but knowledge may be gained that will benefit others.

#### **PAYMENT FOR PARTICIPATION**

At the completion of all study visits and procedures, participants in each cohort will be paid \$225 for the time spent in the clinic. The number will be broken down into two payments of \$100 after visit 1 and \$125 at the completion of the study. This compensation is in line with all the other studies conducted at the Pennington Biomedical Research Center.

#### **EMERGENCY CARE AND COMPENSATION FOR RESEARCH-RELATED INJURY**

No form of compensation for medical treatment is available from the Pennington Biomedical Research Center. In the event of injury or medical illness resulting from the research procedures the research volunteer (from any group) will be referred to their physician/surgeon or a treatment facility. The Pennington Biomedical Research Center is a research facility and provides medical treatment only as part of research protocols. Should a volunteer require medical treatments, community physicians and hospitals must provide them to him/her.

